Objective 1. Evaluate changes in the metabolic and lipid profile:

- Objective 1a. To evaluate changes in the lipid profile (total cholesterol, LDL-C, HDL-C, triglycerides) at week 24 compared to baseline.
- Objective 1b To evaluate the number, size and composition of lipoprotein particles by proton magnetic resonance spectroscopy at week 24 compared to baseline.
- Objective 1c. Percentage of people with increased high-density lipoprotein (HDL) levels >5%.
- Objective 1d. To assess changes in the anthropometric profile (weight, body mass index, abdominal circumference) at week 24 compared to baseline.

Aim 2. Assess changes in he profile inflammatory and of immunoactivation :

- Aim 2a. Assess the changes in the activation immune of the T cell compartment at week 24 compared to baseline.
- Objective 2b. Percentage of patients with reduced inflammatory and bacterial translocation markers at week 24 compared to baseline.

Objective 3. To evaluate changes in arterial stiffness levels measured by pulse wave velocity at week 24 compared to baseline.

Aim 4. Proportion of Participants with decline of >20% of TMAO in the week 24 compared to baseline.

Aim 5. Proportion of Participants with increase of >2 points in the scale MEDAS adherence to the Mediterranean diet at week 24 compared to baseline

Objective 6. Proportion of participants who improve in the quality of life questionnaire. EQ-5D life at week 24.

Objective 7. Evaluate the persistence of all changes included in objectives 1 to 6 at week 48 (24 weeks after the end of the intervention)

Objective 8. To assess the burden of subclinical atherosclerotic coronary disease and changes 1 year after intervention.

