5.3. Definition of the variables of study

Main Variables

- Total cholesterol, cLDL , cHDL , triglycerides in mg/ dL . It will be measured at baseline, week 24 and 48.

Secondary Variables

- Number, size and composition of lipoprotein particles by proton magnetic resonance spectroscopy at baseline, week 24 and 48.
- Anthropometric profile (weight, body mass index, abdominal circumference) at baseline, week 24 and 48.
- CD 3,CD 45,CD4,CD8,CCR7,CXCR3,CCR6,CD103,FOXP3,CD25,CD45RA and CD45RO. Quantification in blood in visits basal, 24 weeks and 48 weeks of cells with markers.
- IL-6, TNF-alpha, IFN-gamma, sCD163, sCD14, MADCAM-1, sCD14 and LPS. Quantification in serum in visit basal, 24 weeks and 48 weeks of
- Rigidity arterial extent by the speed of vole of pulse in the visit basal, week 24 and 48.
- Levels of Trimethylamine -N-Oxide serum (TMAO) in the in the visit basal, week 24 and 48.

- Scale MEDAS of adherence to the diet Mediterranean measures in the Baseline visit, week 24 and 48
- Questionnaire of quality of life EQ-5D in the visit basal, week 24 and 48.
- Presence of atheromatous plaque at the coronary level at the baseline visit and at week 48
- Presence of calcium, fibrous and fatty fraction in the coronary plaque at the baseline visit and at week 48
-

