 - Task 2b. With the samples of serum obtained and preserved to -80°C and when recruitment and monitoring have been completed, the analysis of the lipoprotein subclass profile will be performed by means of Proton Nuclear Magnetic Resonance (NMR) in Metabolomics Platform IISPV, CIBERDEM. Rovira i Virgili University, Biofer Teslab. Lipoprotein analysis of serum samples will be performed using Liposcale® (Biosfer Teslab, Reus, Spain), a method based on 2D diffusion-ordered ^1H -NMR spectroscopy. This protocol evaluates lipid concentrations, particle size and number of three different classes of lipoproteins (vLDL), LDL and HDL), as well as the number of particles of nine subclasses (large, medium and small vLDL , LDL and HDL). This technique records 2D ^1H MRN spectra on a BrukerAvance III 600 spectrometer, operating at a proton frequency of 600 MHz to 310 KHz (Bruker (BioSpin , Rheinstetten , Germany). The signal obtained makes it possible to determine the nine lipoprotein subclasses. (J. Clin. Med . 1875.) The study of lipoprotein subclasses makes it possible to obtain a profile that, when compared with a population database, makes it possible to estimate cardiovascular risk based on the lipid composition of the lipoprotein subclasses in a more specific way than by means of the classic scales for estimating cardiovascular risk.
- Task 3. Measurement of arterial stiffness by pulse wave velocity (to achieve objective 3). Arterial pulse wave velocity will be determined by sequential applanation tonometry (Millar Tonometer, SPC-301; Millar Instruments, Houston, TX) in the carotid and femoral arteries synchronized with a three-lead electrocardiogram using the SphygmoCor device (SphygmoCor ; AtCor , Sydney , Australia). Wave arrival latency time will be calculated using a foot-wave method. The surface distance from the suprasternal notch to each recording point will be measured. Total transit distance will be calculated by subtracting the distance between the sternal notch and the carotid from the distance between the sternal notch and the femoral artery. Arterial pulse wave velocity will be calculated using total transit distance divided by time. of latency. HE will reject the measurements of the speed of the wave pulse that do not meet the automatic quality controls specified by SphygmoCor software . Two pulse wave velocity measurements will be averaged for each subject for all calculations.

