7. PERIOD OF THE STUDY

For can carry to cape all he project it we have divided in different stages:

1. Preparation and validation of the protocol. Patient preselection circuits and diagnostic tests.

January 2025 to February 2025.

This phase will be carried out by the researchers: Design of the patient selection circuit within the HIV unit and promotion of the study among the professionals of the unit focused on the need to address the optimization of the lipid profile of this group of people. We will review the processing of the samples (labeling of the samples, contact with the BioBank service , presentation of the study to the doctors for their knowledge). An anonymous registry of candidate patients will be created.

2. Recruitment of patients

From March 2025 to March 2026. It is estimated that it will take at least one year to recruit the 100 patients.

Recruitment will be carried out at the Infectious Diseases Service of Hospital del Mar (HM). The referent will be [name] [name] (IP). The researchers who will coordinate the recruitment process will be [name]. Patients who meet the inclusion criteria will be referred to a specific consultation created ad hoc to carry out the selection visit. This phase will be carried out interchangeably by [name], [name], [name], [name] or [name] [name]. During this visit, informed consent will be signed, the first sample will be extracted for the complete analysis and general data will be collected: background, history of HIV infection, treatment history and the questionnaires and the participant will be randomized.

3. Follow-up of the patient during 48 weeks. From March 2025 to October 2026.
At this stage, the specific intervention itself will be carried out. Nutritionist researcher [name] together with [name] and [name] [name] from the Endocrinology service will carry out a complete nutritional assessment. Anthropometric measurements and a measurement of the speed of movement will be carried out. of the vibe of pulse. HE will perform follow-up according to it notarized.
4. study visits (March 2025 to October 2026). The final study visit with follow-up at 48 weeks will be carried out in all participants. The tests contemplated in the protocol will be carried out. This stage will be carried out by the equipment of the [name] ([name] together with the [name] and [name] [name]).

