5. Sample collection and processing: blood collection and processing to obtain PBMCs , plasma and serum. The processing and conservation of the samples will be carried out in the IMIM laboratory by [name] -[name] and [name].
6. Sample preparation for FACS . Once initial recruitment is complete, preserved samples will be thawed, stained and prepared for FACS ([name], Dra [name]). Data reading and interpretation will be performed by [name] and an external collaborator ([name] (University of California).
7. Sample preparation and shipment to Metabolomics Platform IISPV, CIBERDEM . Rovira i Virgili University , Bisofer Teslab . When the follow-up is completed, samples will be sent (baseline samples , 24 weeks and 48 weeks). weeks) to the Rovira i Virgili University for further processing and interpretation of the results of the lipoprotein subclasses.
8. Preparation and shipment of plasma samples to Middlesex University , London (Dr. laboratory [name]). Once follow-up is complete, samples (baseline, 24-week and 48-week samples) will be sent to the Middlesex Hospital. university for the determination of TMAO according to the described protocol.
9. Analysis and publication of results (from January 2026 (preliminary) to December 2026) will be carried out by the entire research team.

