9. MANAGEMENT OF SAMPLES

As previously described, during the study, blood will be drawn and processed to obtain PBMCs , plasma and serum. The processing and conservation of the samples will be carried out in the IMIM laboratory by [name] - [name] and [name]. When the initial recruitment is completed, the preserved samples will be thawed, stained and prepared to undergo FACS. When the follow-up is completed, samples will be sent (baseline samples , 24 weeks and 48 weeks) to Rovira i Virgili University for further processing and interpretation of lipoprotein subclass results. Likewise, samples (baseline, 24-week and 48-week samples) will be sent to Middlesex University for TMAO determination.

The samples will be pseudo-anonymized and when the study is completed, the remaining samples will be collected in the PSmar biobank .

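### PBMC staining for FACS is triggered by the end of recruitment, before many week-24 and most week-48 samples exist, and no rule keeps a participant's visits in one run

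*Protocol*

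**What the plan says.** Two places in the protocol set the trigger for the cytometry work. Section 7, stage 6: "Once initial recruitment is complete, preserved samples will be thawed, stained and prepared for FACS". Section 9 (Management of samples): "When the initial recruitment is completed, the preserved samples will be thawed, stained and prepared to undergo FACS". Section 7, stage 2 dates recruitment: "From March 2025 to March 2026. It is estimated that it will take at least one year to recruit the 100 patients".

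The same cells are needed at three visits. Section 5.3 lists the cell markers with "Quantification in blood in visits basal, 24 weeks and 48 weeks of cells with markers". Objective 2a in Section 4 is to "Assess the changes in the activation immune of the T cell compartment at week 24 compared to baseline", and Objective 7 is to "Evaluate the persistence of all changes included in objectives 1 to 6 at week 48".

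The other stored-sample assays are scheduled differently:

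- NMR lipoproteins (Section 6, Task 2b): "when recruitment and monitoring have been completed, the analysis of the lipoprotein subclass profile will be performed". Section 7, stage 7 agrees and names all three visits.
- TMAO (Section 7, stage 8): shipped after follow-up ends, with all three visits named.
- Soluble markers (Section 6, Task 5): plasma is stored so that it can be assayed together, and the stated reason is to limit variability.

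Task 4, which describes the cytometry, gives the panel, gating, controls and instrument. It has no rule on which samples share a run.

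**The concern.** A run here means one session of thawing, staining and acquisition. If staining begins when recruitment closes, every baseline sample is available but many follow-up samples are not. The missing ones must be stained later, in other runs. Run then becomes partly tied to visit at week 24 and almost wholly tied to visit at week 48. A systematic difference between runs would look like a change from baseline, which is the quantity named in Objectives 2a and 7.

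The protocol already guards its other stored-sample assays against this, so the cytometry is the exception. The order of laboratory work is also hard to repair afterwards: where run and visit coincide, no statistical model can separate them.

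**Working it through.** The protocol gives no figure for the share of samples outstanding, so there is none to reproduce. The check asks how many follow-up samples exist at the stated trigger.

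**Inputs.** Recruitment runs from March 2025 to March 2026 (Section 7, stage 2), with no days given. Week 24 is 168 days and week 48 is 336 days after baseline. The accrual pattern is not stated, so uniform accrual is an assumption and is varied below.

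**Step 1: uniform accrual.** With N days of accrual, the share not yet drawn on the last recruitment day is min(1, 168/N) for week 24 and min(1, 336/N) for week 48.

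| Recruitment | N (days) | Week 24 not drawn | Week 48 not drawn |
|---|---|---|---|
| 1 Mar 2025 to 31 Mar 2026 | 395 | 42.5% | 85.1% |
| Exactly one year | 365 | 46.0% | 92.1% |
| 31 Mar 2025 to 1 Mar 2026 | 335 | 50.1% | 100% |

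The visit windows widen this to about 41-52% and 83-100%. Recruitment may take longer than a year. At 15 months (N = 457) the shares are 36.8% and 73.5%, and at 18 months (N = 549) they are 30.6% and 61.2%.

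**Step 2: other accrual shapes, 52.1 to 56.4 weeks (L).** For visit week w:

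- Linearly rising accrual: share not drawn = 1 - ((L - w)/L)². Week 24: 67-71%. Week 48: 98-99%.
- Linearly falling accrual: share not drawn = (w/L)². Week 24: 18-21%. Week 48: 72-85%.

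Under every pattern tried, most week-48 samples and a material share of week-24 samples do not yet exist.

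**Step 3: effect on the randomised contrast.** Take a simple model with two runs, all baseline samples in the first, and a follow-up sample in the second with probability f in both arms. Let the second run add d, in units of the SD of the change. The shift has the same expected value (f × d) in each arm and cancels on average in the between-arm difference. If run is ignored, the variance is multiplied by 1 + d² × f × (1 - f). The protocol gives no value for d, so a range is shown.

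| Assumed d | Week 24 (f = 0.425 to 0.50) | Week 48 (f = 0.851 to 1) |
|---|---|---|
| 0.25 | +1.5 to 1.6% | +0 to 0.8% |
| 0.5 | +6.1 to 6.3% | +0 to 3.2% |
| 1.0 | +24 to 25% | +0 to 13% |

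Because f × (1 - f) cannot exceed 0.25, a shift of 0.5 SD adds at most 6.25% under this model, whatever the accrual shape.

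**Step 4: calendar.** The last enrolment falls between 1 and 31 March 2026.

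- Last week-24 visit (+168 days): 16 August to 15 September 2026.
- Last week-48 visit (+336 days): 31 January to 2 March 2027.

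Section 7, stage 4 ends the visits earlier: "study visits (March 2025 to October 2026). The final study visit with follow-up at 48 weeks will be carried out in all participants". Analysis is to end in December 2026 (stage 9). Closing recruitment early enough to meet the October date would not help the cytometry. The latest enrolment with week 48 by 31 October 2026 is 29 November 2025, which is 39 weeks after 1 March 2025. At that trigger 24/39 = 62% of week-24 and all week-48 samples are still undrawn.

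**The case against.** The strongest reply is that the protocol says only when thawing may begin. It does not say that all baseline cells are stained at that moment, or in how many runs. The term for the trigger is undefined, the text reads as a translation, and stage 6 is listed after the follow-up and visit stages, so the end of follow-up may have been meant. Run allocation is often left to a laboratory manual, and Task 4 does require positive and negative controls.

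Part of this stands. The two-run model is an illustration, and its figures would change with more sessions. But a trigger that is only an earliest start still leaves later samples for other runs, with nothing pairing a participant's visits. The recruitment trigger appears twice, and in both sections it stands beside a follow-up trigger for NMR and TMAO. Assay controls are not a rule for allocating samples to runs.

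Two stronger readings are tempting and are not supported:

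- A reader might infer that the comparison between arms is biased. It is not, on average, provided arms are balanced across runs.
- A reader might infer a high rate of false within-arm findings. No such rate can be given: the protocol plans no one-sample test, fixes no number of runs and gives no size for a run shift.

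Nor is the damage certainly irreversible. Section 9 expects leftover samples to go to the biobank, although it does not say of which type.

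**Conclusion.** The concern holds as a flaw in the stated laboratory sequence. Followed literally, staining starts with about 42-50% of week-24 and 85-100% of week-48 samples undrawn under uniform accrual, or about 18-71% and 72-99% under falling or rising accrual over 12 to 13 months. What is exposed is the change from baseline in Objectives 2a and 7, most of all at week 48, by an amount that depends on a run shift the protocol does not quantify. The randomised contrast loses only a little precision: about 6% in variance at week 24 for an assumed shift of 0.5 SD if run is ignored, under the two-run model. The markers are secondary variables, so this is a correction that should be made before baseline cells are thawed. It is not a threat to the trial's main result.

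**What to change.** In Section 7, stage 6 and in Section 9, replace the end of recruitment with the end of follow-up, as already written for NMR and TMAO. Add one rule: each participant's baseline, week-24 and week-48 PBMC samples are stained and acquired in the same run, with both arms in every run, and the run is recorded. The same-run rule is the essential part.

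If week-24 results are wanted sooner, stain baseline and week-24 pairs together after the last week-24 visit, and keep a further baseline aliquot, where available, to stain with week 48. This fits visits ending in October 2026 if recruitment closes by about mid-May 2026 (31 October 2026 minus 168 days is 16 May 2026).

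The cost is wording in two places and an allocation rule for up to 300 samples (100 participants × 3 visits). There are two downsides. Cytometry results come later, although NMR and TMAO already wait as long. Baseline cells will also have been stored 24 weeks longer than the week-24 cells and 48 weeks longer than the week-48 cells. That difference is the same in both arms but coincides with visit, so storage time should be recorded.

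Separately, reconcile the October 2026 end of visits and the December 2026 end of analysis with recruitment to March 2026, which puts the last week-48 visit between 31 January and 2 March 2027.

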8. ETHICS

The study will be submitted to the rules ethical of the Investigation Biomedical in Humans. The study will be conducted in accordance with the ethical principles derived from the Declaration of Helsinki (Fortaleza, Brazil, October 2013). In addition, the study will be conducted in accordance with the protocol, good clinical practice (GCP) in accordance with the guidelines of the International Conference on Harmonization (ICH) and the regulatory requirements for participating institutions. The study will be conducted according to a protocol reviewed by a Committee. The benefits of the study are considered to be in proportion to the risks; and the rights and well-being of the subjects

will be respected.

Patients will be informed and given an approved informed consent form in compliance with GCP. Likewise, all participants will sign the PsMar Biobank consent. Aspects related to confidentiality will follow established regulations. Before including subjects in the study, the researcher will review the information sheet with the potential participant, and if the participant agrees, agrees to participate, the informed consent document will be signed and dated. The researcher will provide a copy of the signed informed consent form to each subject and will keep a copy in the study file. The subject will be informed, as provided for in Organic Law 15/99 on the Protection of Personal Data, that these may be subject to automated processing and of the rights that the study participants have to consult, modify or delete their personal data from the file. The subject will be informed that the database will be handled by the IP using an access code and the name will not appear in the registry. The responsibility of the file global corresponds to the Institute Hospital of the Sea of

Research Institute (IMIM) of Barcelona. This study will comply with the Code of Good Scientific Practices (<http://www.imim.es/imim/cas/c-CBPC.htm>).

No financial compensation is expected for participants or reimbursement of expenses arising from their participation

9. MANAGEMENT OF SAMPLES

As previously described, during the study, blood will be drawn and processed to obtain PBMCs , plasma and serum. The processing and conservation of the samples will be carried out in the IMIM laboratory by [name] - [name] and [name]. When the initial recruitment is completed, the preserved samples will be thawed, stained and prepared to undergo FACS. When the follow-up is completed, samples will be sent (baseline samples , 24 weeks and 48 weeks) to Rovira i Virgili University for further processing and interpretation of lipoprotein subclass results. Likewise, samples (baseline, 24-week and 48-week samples) will be sent to Middlesex University for TMAO determination.

The samples will be pseudo-anonymized and when the study is completed, the remaining samples will be collected in the PSmar biobank .

10. CONFIDENTIALITY OF THE DATA

This study will be carried out in accordance with the General Data Protection Regulation 2016/679 and Organic Law 3/2018, of December 5, on the Protection of Personal Data and the Guarantee of Digital Rights.

Patient recruitment will be carried out in the outpatient clinics of the HIV unit at Hospital del Mar. Once the participant signs the informed consent, he or she will be assigned a study number that will correspond to his or her medical record number. This will be saved in an encrypted file with a password to which the IP will have access.

The database that will be created ad hoc for the study will not include any data that would allow the patient to be identified: no date of birth, no phone number, no medical record number. Only the study ID. This database will be in The RedCap environment will only be accessible to the study's researchers.

Study data must be verifiable with the source data, which requires access to all original records, laboratory reports, and subject records. Confidentiality of data and patient identity will be maintained during and after the study is completed . Only the principal investigator and authorized study personnel will have access to these confidential records.

None fact used in he analysis and later divulgation of the results of the study will contain some identifiable reference to patient names.

Once the study is completed, the results will be communicated to the relevant authorities, as appropriate, in accordance with local legislation. The data generated will also be published in conferences and scientific journals.

